7.1. Populations and subgroups to be analyzed Per Protocol (PP)

All randomized study subjects not rejected over the observation period and having complete data will be the basis of the analysis. Subjects with missing data will be excluded from the analysis. This will be the primary population for the analysis.

8. Analysis

All outcomes will be presented using descriptive statistics, continuous data by the mean, standard deviation and a plot of the pdf. Binary and categorical variables will be presented in tables using counts. R version 4.0.5 will be used for all statistical analysis.

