The population included in this study are pregnant Syrian refugee women between the ages of 18 to 49, who are in their first trimester of pregnancy.

6. 3. 1. Eligibility

Inclusion Criteria:

- Having the status of “Syrian under temporary protection”
- Being in the first trimester of the pregnancy
- Initial prenatal visit
- Age equal or greater than 18 years and less than or equal to 49

Exclusion Criteria:

- Having a citizenship or a status other than “Syrian under temporary protection”
- Not owning a mobile phone
- Being unable to read and write
- Not initial prenatal visit
- Having a chronic disorder or high-risk pregnancy that requires the individual to go to the hospital frequently. Frequently is defined as more than 3 visits post the baseline visit.
- While gestating, those that develop a high-risk pregnancy that requires more than 3 visits post the baseline visit.

6. 4. Sample Size Determination

The primary outcome measure for the power and size calculation is the difference in the mean number of visits among the different arms of the study. We set our target detectable difference in means to be 0.5 or more additional visits. As the maximum standard deviation is 1.5 due to the restricted range of 0 to 3 visits, our target effect size is $0.5/1.5 = 0.33$. Our calculation shows that each arm will need at least 40 patients to have a power of 90% and a two tailed significance level of 0.05. Due to the nature of refugees, we anticipate a high loss due to follow up and other reasons for dropout. Without prior information, we assume a 20% loss rate and therefore inflate the number of patients per arm by 25%. Thus, we plan to enroll 54 patients per arm for a total of 162 individuals. The statistical software G*Power Version 3.1.9.6 available from the UCLA Institute for Digital Research & Education Statistical Consulting website; [G*Power \(ucla.edu\)](http://G*Power (ucla.edu)), was used for the calculations.

6. 5. Randomization Strategy

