8.1. Primary Analysis

The primary analysis will be a standard one-way fixed effect ANOVA comparing the 3 arms. The resulting ANOVA results and the arm means with 95% confidence intervals will be presented.

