8.3. Missing Data

To reduce the loss-to-follow-up risks: participant phone calls and review of hospital records for subjects with missing data will be performed. Currently there are no plans for attempting a multiple imputation analysis.

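### The only analysis population drops randomised women who are removed during follow-up or still have missing data, and no all-randomised or missing-data sensitivity analysis is planned

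*Combined protocol and SAP*

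**What the plan says.** SAP section 7.1, headed as per protocol, states: "All randomized study subjects not rejected over the observation period and having complete data will be the basis of the analysis". It continues: "Subjects with missing data will be excluded from the analysis", and then: "This will be the primary population for the analysis". Neither the SAP nor the protocol defines another population.

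The SAP does not say what rejection means. The exclusion lists in SAP section 6.3.1 and in the protocol's Eligibility section contain one criterion that can apply after allocation: "While gestating, those that develop a high-risk pregnancy that requires more than 3 visits post the baseline visit".

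The plan does try to limit loss. Section 8.3 says that "participant phone calls and review of hospital records for subjects with missing data will be performed". Section 6.2 adds chart review for women in either control arm who cannot be reached. Section 8.3 then says that multiple imputation is not currently planned. Section 8.1 gives the only between-arm analysis: "The primary analysis will be a standard one-way fixed effect ANOVA comparing the 3 arms". Section 8.2 is a risk-factor regression.

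Section 6.4 expects high loss and allows for it in the sample size: "Without prior information, we assume a 20% loss rate".

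**The concern.** Randomisation makes the arms comparable at allocation. Removing women afterwards keeps them comparable only if removal is unrelated to arm, or unrelated to visits. The plan leaves both routes of removal open.

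- **Rejection.** The likely meaning is the high-risk criterion. It is expressed in visits, the same units as the primary outcome. Because section 7.1 does not cite it, staff in an open-label trial have no written rule for who leaves the analysis.
- **Missing data.** The effort to learn the outcome differs by arm. The reminder arm gets weekly app queries for a month after each appointment date, plus a final call. Controls get contact at the end of the study, with chart review if they are not reached. For the uninformed control arm the documents conflict: SAP 6.1 says hospital records, SAP 6.2 says the women will be contacted, and the protocol's Arms and Interventions section says that no contact details are collected.

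What is at stake is whether the single primary comparison can be read as a comparison of the groups as randomised. As planned, no reported analysis would let a reader judge that.

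**Working it through.** **1. The plan's own figure.** With three arms, Cohen's f = 0.33 and alpha 0.05, the noncentral F distribution gives power 0.902 at 40 per arm, so the stated 40 reproduces. Enrolling 54 and losing 20% leaves 54 × 0.8 = 43.2, about 43 per arm, with power 0.92 on the same inputs. On the plan's own terms the numbers are covered. Inflation restores numbers but does nothing about bias. (Whether 0.33 should have been entered as f is a separate matter.)

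**2. Inputs.** From section 6.4: target difference 0.5 visits, SD 1.5, range 0 to 3, 54 per arm, 20% loss allowance. Assumed, because the documents give neither: loss by arm, and the visit deficit of lost women (gap = retained mean − lost mean). An SD of 1.0 is added as an alternative, since 1.5 is the maximum on a 0 to 3 range.

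**3. Bias from deleting lost women.** In each arm, the mean over all randomised women = retained mean − loss × gap. Hence bias in (reminder − control) = loss_R × gap_R − loss_C × gap_C.

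| Loss, reminder v control | Gap 0.5 | Gap 1.0 |
|---|---|---|
| 20% v 20% | 0 | 0 |
| 30% v 10% | 0.15 − 0.05 = +0.10 | 0.30 − 0.10 = +0.20 |
| 10% v 30% | −0.10 | −0.20 |
| 15% v 5% (half recovered) | 0.075 − 0.025 = +0.05 | 0.15 − 0.05 = +0.10 |
| 5% v 15% (half recovered) | −0.05 | −0.10 |

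Against the 0.5 target, the half-recovered rows are 10 to 20%.

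**4. Against sampling error.** The standard error of a two-arm difference at 43 per arm is SD × √(2/43): 0.323 at SD 1.5 and 0.216 at SD 1.0. Every bias in the table is smaller.

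**5. Effect on the planned ANOVA, half recovered.** Both control arms are given the same loss.
- No true effect, 51/46/46 or 46/51/51 analysed: rejection is 5.3 to 7.5%, against a nominal 5%.
- True benefit of 0.5 over both controls, reminder arm better followed (51/46/46): power falls from 38% to 31% or 25% at SD 1.5, and from 72% to 62% or 52% at SD 1.0.

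**6. What would reverse an observed 0.5.** Suppose 20% of each arm is truly missing. The all-randomised difference is 0.8 × 0.5 + 0.2 × x, where x is the difference (reminder − control) among lost women. It is zero at x = −0.4/0.2 = −2.0. At 10% missing, x = −0.45/0.1 = −4.5, which a 0 to 3 range cannot produce.

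**7. The high-risk criterion.** The documents give no incidence by arm, so its effect is not sized here. If reminders do not change who is classed as high-risk, randomisation balances these removals and they do not bias a comparison of the women who remain.

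**The case against.** The case for leaving the plan alone has substance. Calls and record review apply to subjects with missing data in general, and both control arms have chart review as a fallback, so residual loss may be small. The unequal loss in the working is assumed, and the resulting biases are modest. If the reminder arm is the better followed and lost women attend less, the error runs against the app. All of this stands, and it limits the severity. It does not remove the gap: women still missing are deleted, and nothing planned would show whether that mattered.

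A reader might infer more than the documents support, in three ways.

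- **That the planned 20% loss could reverse the result.** The worst-case range for an observed 0.5 at 20% missing is 0.4 ± 0.6, or −0.20 to 1.00. Its lower end requires every lost reminder woman to have attended 0 visits and every lost control 3. The 20% is also a sample-size allowance made without prior information. It covers other dropout as well, and is not stated to be what remains after calls and record review.
- **That women are removed on the outcome itself.** The criterion turns on visits a pregnancy requires, not on visits attended, so reminders need not affect it.
- **That one blank item on the 16-item form removes a woman from the ANOVA.** Complete data is undefined, but the ANOVA needs only arm and visit count, and section 8.3 treats missing data as loss to follow-up. A definition settles this.

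**Conclusion.** The concern holds as a gap in the plan, not as evidence of a wrong result. The sole and primary population is selected after randomisation, by a rejection rule that is not defined and by deletion of women still missing. No all-randomised or missing-data sensitivity analysis accompanies it.

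The size is illustrative. It is zero under equal loss and equal deficits, 0.10 to 0.20 visits at 30% v 10% loss, and 0.05 to 0.10 if half are recovered. This rests on assumed loss by arm and on lost women attending 0.5 to 1.0 fewer visits. The direction is not fixed: the benefit is understated if the reminder arm is better followed, and overstated if it loses more women.

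Reversing an observed 0.5 at 20% truly missing per arm would need lost reminder women to attend more than 2.0 fewer visits than lost controls, so the worst-case bound is not the reason to act. The reason is that a cheap change in wording restores the randomised comparison and lets the reader see the effect of loss. It should be made before outcomes are seen.

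**What to change.** **Section 7.1.** Make the primary population all randomised women, in their assigned arm, with a known post-baseline visit count, including those who become high-risk after allocation. Define complete data as a known visit count. Keep the current set, with rejection defined, as a sensitivity analysis.

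**SAP 6.3.1 and protocol Eligibility.** Add one sentence to each list: the criterion that applies during gestation does not remove a randomised woman from the primary analysis.

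**Section 8.3.** After calls and record review, add one missing-data sensitivity analysis covering all randomised women: multiple imputation using arm and baseline items, with arm-specific shifts of 0.5 and 1.0 visits. Report exclusions and missingness by arm and reason.

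**SAP 6.1, SAP 6.2 and protocol Arms and Interventions.** Reconcile how outcomes are obtained in the uninformed control arm.

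**Cost.** A few sentences and a short R script, with a little more analysis work. High-risk women with more visits would stay in. Section 6.4 argues "As the maximum standard deviation is 1.5 due to the restricted range of 0 to 3 visits", so counts above 3 could raise the SD and widen the intervals.

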8.1. Primary Analysis

The primary analysis will be a standard one-way fixed effect ANOVA comparing the 3 arms. The resulting ANOVA results and the arm means with 95% confidence intervals will be presented.

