5.1. Background and Rationale of the Study

According to the UN, The Syrian refugee crisis is the worst humanitarian crisis since World War 2^[1]. Since the start of the Syrian Civil War in 2011, 12 million Syrians have been forcibly displaced from their homes. Turkey hosts nearly 4 million of these refugees, which constitutes the largest population of refugees in the world.^[2] Healthcare services are free in Turkey for the Syrian refugee population through national insurance; however, demand-side barriers such as language, not knowing where to receive care, and fear of deportation persist. Pregnant Syrian women are especially vulnerable to barriers to care. Peer-reviewed studies in Turkish hospitals indicate that refugee women are more likely to die during and after labor^[3]; additionally, less than 50% of pregnant Syrians attend at least four prenatal care visits^[4].

A robust body of research evidence supports the use of mobile phone-based reminder platforms to increase timely, complete access to health services. Mobile phone-based reminders have been shown in randomized controlled trials and systematic reviews to increase the uptake of various

services, including prenatal care.^{[5][6]} A systematic review found that the majority of text message reminder interventions improved health outcomes.^[7] Mobile phone penetration is high among Syrian refugees in Turkey^[8] and qualitative studies demonstrate that mobile health interventions are acceptable and feasible for Syrian refugees.^[9]

5. 2. Objectives

The primary objective of this study is to evaluate the impact of mobile phone-based reminders on the uptake of prenatal care among pregnant Syrian refugee women. More specifically, the study assesses the effectiveness of mobile phone-based reminders by measuring the percent increase in the number of prenatal appointments attended by intervention arm participants compared to the control arm participants.

5. 3. Hypotheses

Null hypothesis: Sending reminders on participants' upcoming appointments 2 weeks before, 1 day before, and on the day of the appointment will not have any effect on the number of appointments that are attended. Thus, the mean number of visits will not vary significantly across the 3 arms.

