Alternative hypothesis: Sending reminders on participants' upcoming appointments 2 weeks before, 1 day before, and on the day of the appointment will result in a percent increase on the number of appointments that are attended by the intervention group compared to the control groups.

6. Study Methods

6. 1. Study Type

This is a behavioral intervention study using an unblinded, parallel groups, randomized controlled study design. The intervention group ("Reminder") will download and use the HERA application to receive appointment reminders through push notifications. The control group ("No reminder") will not be using the HERA application, and therefore won't be provided with any reminders. The third group will also be a non-notified control group, i.e., "No reminder" as well.

The third group's data will be collected retrospectively via hospital records. The intent of the 3rd arm is to estimate the “true” baseline for the number of visits without any extra attention given by the medical staff, in order to prevent inadvertent behavior modification through perceived observation bias.

6. 2. Study Procedure

Pregnant Syrian refugee women who are in their first trimester of pregnancy will be enrolled in the study. Participants will be enrolled from the Obstetrics and Gynecology department of refugee health clinics in Istanbul. Participants will be randomized and enrolled into intervention or either of the two control arms (refer to section 6.5. Randomization Strategy for details).

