For the intervention arm, participants will be given the consent form. After having consented to participate in the study, they will be given the socioeconomic and health history form. In what follows, they will receive a 30-minutes brief about the mobile app HERA and will be asked to download it. The mobile application will automatically plan out the dates of further prenatal care appointments based on the date of the last menstruation. Participants will receive reminders in the form of push notifications for prenatal checkup dates for 6 months. Reminders will be sent at the following intervals: 1) 2 weeks before, 2) 1 day before and 3) on the day of the recommended appointment. After the recommended appointment date, participants will receive push notifications asking whether or not they went to the appointment in weekly intervals for 1 month. This reminder algorithm will be used for each prenatal checkup for a total of three appointments post the baseline visit: once in second trimester and two in third trimester, using the World Health Organization and Turkish Ministry of Health prenatal checkup calendar. At the end of 6 months of follow up time, participants in the intervention arm will be contacted via phone call to ask for any remaining appointments or unanswered notifications. Completeness of 3 prenatal care appointments post the baseline visit, as recommended by WHO and implemented by Turkish MoH will be compared to the control groups.

Participants in the informed control arm will be given the consent form and will be asked for their contact information if consented. They will also be given the socioeconomic and health history form. Participants in the non-informed control group just will be given the socioeconomic and health history form. Both the informed and non-informed control group members will be

reached out at the end of the 6-month study period to be asked about the number of prenatal care appointments they attended. If unable to be reached, retrospective chart review of the participant's medical record will be attempted, in order to obtain the number of attended prenatal care appointments.

6. 2. 1. Recruitment Strategy

Participants will be enrolled from the obstetrics and gynecology department of refugee health clinics in Istanbul, Turkey with the help of a translator (Turkish to Arabic). The enrollment will take place with the help of the physician.

6. 3. Study Population

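### The primary analysis is a three-arm omnibus F test with no named reminder-versus-control contrast, so a significant result would not show that reminders work

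*Combined protocol and SAP*

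**What the plan says.** Section 8.1 is the whole primary analysis. The test is given as "The primary analysis will be a standard one-way fixed effect ANOVA comparing the 3 arms", and the reporting as "The resulting ANOVA results and the arm means with 95% confidence intervals will be presented". Both the test and the intervals concern the three arms as a set or one at a time; no between-arm difference appears.

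Elsewhere the aim is a comparison with control:

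- Section 5.2 describes the study as "measuring the percent increase in the number of prenatal appointments attended by intervention arm participants compared to the control arm participants".
- The alternative hypothesis in 5.3 is that reminders "will result in a percent increase on the number of appointments that are attended by the intervention group compared to the control groups".
- Section 6.2 says that completeness of the three post-baseline visits, "as recommended by WHO and implemented by Turkish MoH will be compared to the control groups", without a method or a choice of control.

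The null hypothesis in 5.3 has two parts. The first is that reminders "will not have any effect on the number of appointments that are attended". The second is drawn as a consequence: "Thus, the mean number of visits will not vary significantly across the 3 arms". Section 6.1 explains that the third, uninformed arm is included "in order to prevent inadvertent behavior modification through perceived observation bias", and both 6.1 and the protocol's arm description treat it as the true baseline.

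The Poisson model in 8.2 covers sociodemographic and medical history factors. Section 7 refers to other risk factors, which may imply that arm is in that model, but 8.2 does not name it.

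**The concern.** The F test holds its 5% level for equality of three means. The trial's question is whether reminders have an effect. The two nulls coincide only if the informed and uninformed controls have the same mean, and the stated reason for the third arm is that they may not. The second sentence of the null therefore does not follow from the first.

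Two things are at stake. First, a significant F could come from observation alone, and the SAP does not say which contrast then decides. Second, the choice among informed, uninformed and pooled controls would be made after the data are seen. These comparators answer different questions. Reminder versus uninformed control mixes any reminder effect with the effect of being observed; reminder versus informed control removes the part of the observation effect that both arms share. The percent increase named in the objective would have no planned estimate or interval.

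**Working it through.** **Inputs.** From 6.4: target difference 0.5 visits, SD 1.5, two-tailed 0.05, 40 evaluable per arm, 54 enrolled per arm, 20% loss (54 × 0.8 = 43.2, so 43 evaluable). From 8.1: one-way ANOVA, three arms. Assumed, because the documents give no value: the gap h by which both observed arms exceed the uninformed arm (0.25 or 0.5 visits), and an alternative SD of 1.0.

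**The plan's own figure.** An omnibus three-group F test with 0.33 entered as Cohen's f gives power 0.902 at 40 per arm and 0.894 at 39, so the stated 40 is reproduced. The sample size, like 8.1, was built on the omnibus test.

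**Observation effect only.** Order the means as uninformed, informed, reminder. With no reminder effect they are (0, h, h). The noncentrality is λ = n × Σ(mean − grand mean)² / SD², and for this pattern the sum of squares is 2h²/3.

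- h = 0.5, n = 40, SD 1.5: λ = 40 × 0.1667 / 2.25 = 2.96. With 2 and 117 df the critical F is 3.07 and the rejection probability is 0.311.
- For a true reminder effect with equal controls, (0, 0, 0.5), the sum of squares is the same, so λ is 2.96 and rejection is again 0.311. The test cannot tell the two patterns apart.

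Probability that F rejects when reminders do nothing:

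| SD | gap h | n = 40 | n = 43 |
|---|---|---|---|
| 1.5 | 0.25 | 0.108 | 0.113 |
| 1.5 | 0.5 | 0.311 | 0.332 |
| 1.0 | 0.25 | 0.190 | 0.202 |
| 1.0 | 0.5 | 0.621 | 0.655 |

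These are omnibus rejection rates, not rates of false claims for reminders.

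**What might then be claimed.** Simulation with 400,000 runs, pooled variance, 3(n − 1) df, SD 1.5, no reminder effect:

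| Event | h = 0.25, n = 40 / 43 | h = 0.5, n = 40 / 43 |
|---|---|---|
| F significant and reminder arm highest | 5% / 6% | 16% / 17% |
| F significant and at least one of informed, uninformed or pooled favours reminders at p < 0.05 | 7% / 7% | 24% / 25% |
| Pre-named reminder versus informed control favours reminders, no gate | 2.5% / 2.5% | 2.5% / 2.5% |

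At h = 0.5 nearly all of the second row is reminder versus uninformed control (0.235 of 0.236 at n = 40). Those means truly differ; the error is attributing the difference to reminders.

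**All arms equal.** Choosing freely among the three comparators without the F test gives 9.6% two-sided. With the F test applied first it is about 4%.

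**Bounded outcome.** With visits restricted to 0 or 3 and means 1.0, 1.5, 1.5 (60,000 runs), F rejects in 0.337 (n = 40) and 0.345 (n = 43), so the normal-theory figures are not an artefact.

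**The case against.** The strongest defence is internal consistency. The second sentence of the null, the sample-size section and 8.1 all refer to three arms, and F is valid for that null. Rejecting when the means differ is correct behaviour. This is true, but rejecting that null does not establish the alternative hypothesis or answer the objective.

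A second defence is that the plural control groups could mean superiority to both. On that reading, with F significant as well, reminders would be wrongly favoured in about 1.1% (h = 0.25) or 1.9% (h = 0.5) of trials. The reading is reasonable, but it is not written down, and nothing excludes the others.

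Third, the gap is assumed, and 0.5 equals the whole target effect. At a gap of 0.1 and SD 1.5, F rejects in only about 6%. The size of the problem is therefore uncertain. Its existence rests on the plan's own rationale for the third arm.

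Fourth, arm means, SDs and ANOVA results will be reported, so differences can be derived: at SD 1.5 the 95% half-width is 1.979 × 1.5 × √(2/43) = 0.64 visits. That recovers the estimate but not the pre-specification. Coded analysis under 6.5 does not help either, since it does not say which contrast decides once the codes are opened.

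One point stands as a caution about the remedy. Under 6.2 only the reminder arm gets the 30-minute briefing and weekly attendance questions. Reminder versus informed control holds 5% only if observation acts equally in both arms. If the extra contact alone added 0.25 visits, that contrast would favour the reminder arm in 12% of trials (SD 1.5, n = 43).

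**Conclusion.** The concern holds and should be corrected before the codes are opened. Followed as written, the primary analysis cannot distinguish a reminder effect from an observation effect, and the deciding comparison is left open. That conclusion needs no assumed gap; it follows from 8.1 set against 5.2, 5.3 and 6.1. With all arms equal, the F test read first contains the multiplicity, so the main residual risk is misattribution. Its size depends on the unknown gap between controls: at SD 1.5, a post-hoc choice of comparator after F favours reminders in 7% (gap 0.25) to about 25% (gap 0.5) of trials in which they do nothing, against 2.5% for a pre-named reminder-versus-informed contrast under equal observation effects.

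**What to change.** In 8.1, name one primary contrast from the same ANOVA model: the reminder-minus-control difference in mean visits with a 95% CI, against a stated comparator. Informed control removes an observation effect that is equal in both arms. If the sponsor prefers the uninformed arm, the SAP should say that the contrast includes that effect. Then choose one route:

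- **(a) Fixed order:** the primary contrast at two-sided 0.05, then (with informed control as the comparator) reminder versus uninformed, then informed versus uninformed.
- **(b) Gate:** the F test first, then all three pairwise tests, which controls familywise error for three groups.

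Report the percent increase as a ratio of means with a 95% CI by a named method, for example the delta method on the log ratio with arm-specific variances; Fieller or a log-link model with robust errors would also serve. Reword the second sentence of the null in 5.3 to match the contrast, and refer to it in 6.2. To keep the coding in 6.5, run all three contrasts on codes 0, 1 and 2 and read off the named one when the codes are opened.

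**Cost.** SAP wording and a few lines of R; no new data. Under (a), later contrasts are blocked if the first fails: with a true 0.5-visit effect and equal controls, step two succeeds in 17% of trials at SD 1.5 and 44% at SD 1.0 (n = 40), or 19% and 48% (n = 43). Under (b), power for reminder versus informed control at n = 40 falls from 31% to 23% at SD 1.5 and from 60% to 53% at SD 1.0; at n = 43 and SD 1.5 it falls from 34% to 25%. Pooling the controls would give 40% at SD 1.5 and n = 40 if they are equal, but does not hold 5% if they differ. The shortfall of all these figures against the stated 90% is a separate sample-size problem that this change neither causes nor cures.

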Subjects will be selected on the following basis: randomly select a week and recruit on 6 days of that week. On 3 of the days the selection process will start in the morning, denoted as AM, (the first part of the day that is expected to see half of the patients) and on the other 3 days the selection process will start in the afternoon, denoted as PM, (the second part of the day that is expected to see half of the patients.) For each AM/PM session, the first 27 subjects giving approval to be in the study will be randomly assigned into one of the 3 arms. It is estimated that 100 to 200 women use the hospital daily. Thus, we feel that most likely the daily target intakes will be met. However, if not met by the end of the AM/PM shift, the selection process will stop. After day 6 and before any data analysis, a check will be done on the sample sizes and additional subjects may be recruited by selecting another week to perform additional recruiting.

This sampling plan requires that the number of women coming to see the medical staff be approximately the same day to day and AM to PM.

Details of the random assignment to AM/PM and to groups are attached. The assignment of treatment and control groups to 0, 1 or 2 will be done prior to the start of subject recruitment but will not be shared with the data analyst until after the analysis is complete.

7. Outcomes

Primary Outcome:

The primary outcome of this study is the number of medical visits, following the initial baseline PNC visit, over the 6-month period prior to childbirth.

Secondary analyses:

In the secondary analyses, we will further examine other risk factors, including sociodemographic and reproductive medical history, on the number of medical visits during the study period. The following additional data will be gathered:

1. Age
2. Highest level of education
3. Current employment status and profession if employed
4. Marital status
5. If married, whether the spouse is alive or deceased
6. If married, whether the spouse resides with the participant or not
7. Number of children
8. Ages of children
9. Miscarriage history, and the number and the timing of miscarriage, if any
10. Number of deceased children, if any
11. Number of times the participant gave birth to stillborn baby, if any
12. If prior pregnancies, the number of deliveries occurred at home and at a hospital
13. Type of delivery (vaginal, C-section) and the number of each type

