14. Information on prenatal care appointments made during prior pregnancies, and the number of appointments attended
15. Information on medical conditions that require long-term medication use, if yes, the name of the condition and medication
16. Duration of time living in Turkey

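### The primary ANOVA adjusts for neither recruitment session nor earlier prenatal attendance, which may cost precision but does not bias the comparison

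*Combined protocol and SAP*

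**What the plan says.** SAP 8.1 gives the whole primary analysis: "The primary analysis will be a standard one-way fixed effect ANOVA comparing the 3 arms", reported as the ANOVA result and arm means with 95% confidence intervals. There is no term for session, day or AM/PM, and no baseline covariate.

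SAP 6.5 recruits on six days, three starting in the morning and three in the afternoon. In each session, "the first 27 subjects giving approval to be in the study will be randomly assigned into one of the 3 arms". Six sessions of 27 make the planned 162. Further details of the assignment are said to be in an attachment.

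Among the baseline data, SAP section 7 lists as item 14: "Information on prenatal care appointments made during prior pregnancies, and the number of appointments attended". Question 14 of the Sociodemographic and Health History Form collects this, but asks about the previous pregnancy only. The one planned use of these factors is the Poisson regression in SAP 8.2. That is a search for factors influencing visit number, and it does not say that arm is in the model.

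SAP 7.1 excludes subjects with missing data from the analysis.

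**The concern.** Attendance in an earlier pregnancy is the closest baseline measure the trial has of the behaviour it is trying to change. SAP section 7 itself groups the history items with other risk factors for visit number. Session is the unit within which women are assigned. In an arm-only ANOVA, any variation in visits that these variables explain stays in the error term, so standard errors are larger than they need to be.

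The stake is efficiency in a small trial: after the assumed 20% loss, about 43 women per arm remain. There is also a stake in prespecification. If no adjusted comparison is written down now, any that appears later will have been chosen after the data were seen.

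**Working it through.** **Inputs from the documents (SAP 6.4 and 6.5).** Difference 0.5 visits; SD 1.5, stated as the maximum for a 0 to 3 range; two-sided 0.05; 54 enrolled per arm; 20% loss; 6 sessions of 27. Evaluable women: 54 × 0.8 = 43.2, taken as 43 per arm.

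**Assumed, because the documents do not give them.** R-squared of session and earlier attendance together, 0 to 0.30. SDs of 1.0 and 1.2 are shown beside the plan's 1.5.

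**The plan's own figure.** SAP 6.4 says "each arm will need at least 40 patients to have a power of 90% and a two tailed significance level of 0.05". A three-group ANOVA with noncentrality N × f² and f = 0.33 gives 40 per arm (power 0.902), so the figure reproduces. It does so only when 0.5/1.5, a standardised difference between two means, is entered as Cohen's f. With one arm 0.5 above two equal arms and SD 1.5, f is 0.157, power at 40 per arm is 31%, and 172 per arm would be needed for 90%. That is a separate problem, but it shows there is no power to spare.

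**Degrees of freedom.** Arm only: 3 × 43 − 3 = 126. Six sessions use 5 and four attendance categories use 3, which leaves 126 − 8 = 118. The critical t moves from 1.979 to 1.980.

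**Precision.** SE of a difference between two arms = SD × √(2/43) × √(1 − R²). At SD 1.0 and R² = 0 this is 0.2157, and 0.5/0.2157 = 2.318. Power comes from the noncentral t with that noncentrality and error pooled over three arms. The interval width scales by √(1 − R²) and the equivalent sample size by 1/(1 − R²).

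| R² | Interval narrower by | Equivalent extra women | Power, SD 1.0 | Power, SD 1.2 | Power, SD 1.5 |
|---|---|---|---|---|---|
| Unadjusted | – | – | 63.3% | 48.3% | 33.5% |
| 0 | 0% | 0% | 63.3% | 48.3% | 33.5% |
| 0.05 | 2.5% | 5% | 65.5% | 50.2% | 35.0% |
| 0.10 | 5% | 11% | 67.9% | 52.4% | 36.6% |
| 0.20 | 11% | 25% | 72.9% | 57.2% | 40.3% |
| 0.30 | 16% | 43% | 78.5% | 62.9% | 44.9% |

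All adjusted rows have the 8 degrees of freedom charged. At R² = 0 the loss of power is less than 0.1 percentage point.

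**Interaction with the complete-case rule.** If a blank answer to question 14 removed a woman under SAP 7.1, the gain could vanish. At SD 1.0 with 39 rather than 43 per arm, power is 64% at R² = 0.10 and 61% at R² = 0.05, against 63% unadjusted with everyone kept.

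**The case against.** A simple ANOVA is a defensible primary analysis for a small randomised trial, and several objections to adjusting have force.

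- **The gain is assumed.** No correlation between earlier and current attendance, and no between-session variance, appears in the documents. R² = 0.30 means a multiple correlation of 0.55 (√0.30), which is a lot to expect from one recalled item in categories plus session. This stands, so the range has to start at zero.
- **Session may be irrelevant.** Nothing suggests that day or AM/PM predicts visits. SAP 6.5 does not say that the list is blocked or stratified by session, and the attachment is not in the text available. This also stands. Session enters the model because assignment is made within it, subject to that attachment; earlier attendance is the stronger reason for adjusting.
- **The covariate is imperfect.** It has no value in a first pregnancy, and no question asks directly whether this is one. A previous pregnancy that ended early would count as low attendance. These reduce the gain; they do not make adjustment unsound.
- **The third arm may lack it.** SAP 6.1 says this arm's data are collected retrospectively from hospital records. SAP 6.2 and the protocol's arm descriptions say that these women fill in the form. Until that is settled, the covariate might be absent or measured differently in one control arm.

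Two stronger inferences should be resisted. A reader might conclude that the ANOVA is invalid because it ignores how women were assigned. Under randomisation the unadjusted comparison stays unbiased, and with sessions balanced by arm it is, if anything, conservative. A reader might also conclude that precision is certainly being thrown away at no cost to recover. The documents cannot show that either.

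**Conclusion.** The point holds as a conditional loss of efficiency. The primary model omits two variables that the design or the baseline form supplies, and no adjusted arm comparison is planned. If they are prognostic, intervals are wider than necessary, by an amount the documents do not determine: intervals could be 0% to 16% narrower over R² of 0 to 0.30. The figures rest on that assumed range, on 43 evaluable women per arm, and on nobody being lost because of the covariate.

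The case for changing the plan is the asymmetry: almost nothing is lost at R² = 0, and there is a moderate gain otherwise. Adjustment does not rescue the sample size. At the plan's SD of 1.5, even the most favourable case shown leaves power for reminder against one control at 44.9%. This is a recommended improvement, not a condition for the trial's validity.

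**What to change.** Before any analysis, amend SAP 8.1 as follows.

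1. Make the primary analysis a linear model of visits on arm, earlier-attendance category and recruitment session. Use four attendance categories: no earlier pregnancy, fewer than four visits, four or more, and missing or unknown. State that a blank answer to question 14 does not exclude a woman under SAP 7.1.
2. Check the session term against the attached assignment scheme, and allow more levels if a further week is used.
3. Report adjusted reminder-minus-control differences with 95% confidence intervals. SAP 6.5 withholds the arm codes from the analyst, so all pairwise differences can be produced under the codes and labelled afterwards. Keep the unadjusted ANOVA as supporting.
4. Reconcile SAP 6.1 with SAP 6.2 and the protocol's arm descriptions, so that earlier attendance is collected in the same way in all three arms. The missing category is safe only if missingness does not depend on arm.
5. Align SAP item 14 (prior pregnancies) with form question 14 (previous pregnancy), and state how no earlier pregnancy is derived from the items on children, miscarriage and stillbirth.

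The cost is SAP wording, about 8 degrees of freedom and some noise in a recalled covariate. If R² is near zero there may be no gain. No new data item is needed, provided the form is completed in the third arm.
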